Title: The Articulated Oral Airway as an Aid to Mask Ventilation, a Prospective Interventional, Non-Inferiority Study

NCT# 03144089

[name]

May 16, 2021

AOA Testing

PI: [name]
IRB ID #: 201704829

Form Content

I. Project Introduction

I.1 *Project to be reviewed by:*
IRB-01

I.2 *Project Title:*
The Articulated Oral Airway as an Aid to Mask Ventilation, a Prospective Interventional, Non-Inferiority Study

I.3 *Short Title (optional):*
AOA Testing

I.4 *Provide a short summary of the purpose and procedures of the study proposed in this IRB application.*

- ***DO NOT include information on studies not proposed in this application.***
- ***Use LAY terminology only. This must be easily understandable by IRB community members and nonscientists.***
- ***DO NOT cut and paste technical abstracts from funding applications that may not be understood by a general audience.***

The Articulated Oral Airway (AOA) is a new, FDA Class 1 (exempt from pre-market notification), device which assists in airway management, specifically mask ventilation. The AOA is currently being developed by the University of Iowa Research Foundation (UIRF Case# 2014-018) in conjunction with the Primary Investigator. The device has gone through two phases of human analog (mannequin) testing, with another round scheduled. After the third round of mannequin testing, bio-compatible (safe for oral use) prototypes will be made in a ISO 9001:2008 Certified molding facility. We plan to test these bio-compatible prototypes in healthy human volunteers to assess real-world function.

Patients who are predicted to be difficult to breath for after going to sleep (and meet inclusion criteria/do not meet exclusion criteria) will be offered enrollment in the study. Those that enroll will have their airway maintained with two different designs of oral airway (soft plastic oral stents) to see if one works as well as the other. To determine this we will be looking at how big a breath is achieved with a set pressure via the ventilator through each device. We will also be examining the devices after removal, and seeing the patients in the recovery room, to evaluate for any difference in oral or throat trauma. As patients will be anesthetized and breathed for regardless of their enrollment status, their day will be no different aside from speaking with a study team member prior to surgery and again in the recovery room.

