I.5 *Specify your research question(s), study aims or hypotheses (do not indicate "see protocol")*

- 1) Does the AOA facilitate mask ventilation (as measured by inspiratory and expiratory tidal volumes and end-tidal CO₂ waveforms) as well as a Guedel oral airway in patients with risk factors for difficult mask ventilation
- 2) Is the AOA non-traumatic as anticipated to the human airway

I.6 *Background and significance and/or Preliminary studies related to this project. (do not indicate "see protocol")*

Brief explanation: The Articulated Oral Airway (AOA) is a novel device in the field of Airway Management which actively facilitates both mask ventilation (breathing for an anesthetized patient without a breathing tube) and fiberoptic intubation (placement of a breathing tube using a flexible

camera). No device currently on the market has this dual functionality. In conjunction with the University of Iowa Research Foundation (UIRF Case# 2014-018) the AOA received US Patent 8,794,230 B2 in August of 2014.

Detailed explanation: A primary goal of all anesthetics is the establishment of a patent airway. The most commonly performed airway management technique is mask ventilation; using a mask over a patient's nose and mouth to breath for them. This technique is made significantly more difficult by certain anatomical features, the most common of which is a large tongue related to obesity. The AOA not only creates a conduit for delivering oxygen and anesthetic agents, but also actively displaces the tongue to optimize the space available for ventilation.

In addition, the AOA can act as a conduit for flexible fiberoptic intubation – a technique of utilizing a flexible guide to navigate airway anatomy and allow placement of a breathing tube ("endotracheal tube," or ETT) with minimal manipulation of a patient's neck and airway. A significant disadvantage of fiberoptic technique is that, for an image to be seen, an "airspace" (a space void of visual obstruction) must be created. If the tip of the fiberoptic scope is touching the patient's airway or any foreign objects in the patient's airway, the result would be analogous to leaving the lens cap on a camera and the necessary anatomy would not be seen.

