- Paper/hard copy records (hard copy surveys, questionnaires, case report forms, pictures, etc.) - Paper/hard copy records (hard copy surveys, questionnaires, case report forms, pictures, etc.) - Case report forms will be kept separate from informed consents in 3 hole punched binder. They will be kept in locked file cabinets in a locked office of one of the research assistants. The CRF will have a study ID number for identification. One data list will be kept of the subjects name and ID number for identification purposed on a password protected document within a password protected file. The intraoperative video will contain no images of the patient or patient identifiers, just the anesthesia monitor and the device randomized to be placed first. The video will be uploaded to a password-protected server (backed up and overseen by UI department of anesthesia ITS) to which only study personnel will have access. After upload, the original video will be deleted.
- Electronic records (computer files, electronic databases, etc.) - Electronic records (computer files, electronic databases, etc.) - One data list will be kept of the subjects name and ID number for identification purposed on a password protected document within a password protected file.
 - Name - [name]
 - Title - Information Technology Security Officer
 - University Job Classification - System Administrator and Systems Programmer II

X.5

Do the confidentiality protections indicated above allow only members of the research team to access the data/specimens?

Yes

X.7

Does your study meet the NIH criteria for a [Certificate of Confidentiality](#) or will you be applying for Certificate of Confidentiality?

No

XI. Data Analysis

XI.1

Describe the analysis methods you will use, including, if applicable, the variables you will analyze

We will use non-inferiority testing for the analysis of the primary outcome variable in this study. We will assume that the Articulated Oral Airway is non-inferior to the Guedel oral airway if the difference in expiratory tidal volume measurements between the two devices is less than 1ml/kg.

XI.2

Provide the rationale or power analysis to support the number of subjects proposed to complete this study.

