We will assume that the AOA is non-inferior to the GDA if the difference in expiratory tidal volume measurements between the two devices is less than 1ml/kg. With a sample size of 55 patients, a paired t-test of equivalence of means with a 0.050 one-sided significance level will have 90% power to reject the null hypothesis that expiratory tidal volumes with a GDA and AOA are not equivalent (> 1ml/kg difference in expiratory tidal volumes) (SD of difference is 2.5ml/kg). To allow for 3 protocol failures, we will recruit a total of 58 patients. Note that, if the non-inferiority is satisfied, we will also explore the superiority of the AOA to the GDA. With this number of patients, the paired t-test will have >95% power to test the hypothesis that the expiratory tidal volumes measured with the AOA are 1.5ml/kg greater than with the GDA (SD of difference: 2.5ml/kg).

XII. Future Research

XII.1

Do you wish to keep any information about subjects involved with this research project so that members of the current research team may contact them in the future for your own research projects?

No

XII.2

Do you wish to keep any information about subjects involved with this research project so that other researchers may contact them for future research?

No

XII.4

Does this project involve storing any data, tissues or specimens for future research?

No

New Project Form Attachments

Attachment Name	Category	Ver	Size	Attached
Articulated Oral Airway study_Informed_consent.rtf	Informed Consent	5	181 E k	06/28/17
Articulated Oral Airway study_Record of consent.rtf	Record of Consent	1	53 k E	04/19/17
[name] GAP 2017 Aluminum Mold Upgrade Request.pdf	Funding Source Grant	1	99 k E	04/18/17
 GAP Funding Proposal (part 2, aluminum molds and biocompatible AOAs)				
[name] GAP-award-letter-forms_3x_FY16 2-1-16.docx	Funding Source Grant	1	287 E k	04/18/17
 GAP Funding Award Letter (Part 1)				
[name] GAP-award-letter-forms_3x_FY17.docx	Funding Source Grant	1	294 E k	04/18/17
 GAP Funding Award Letter (Part 2, aluminum molds a bio-compatible AOAs)				
GAP Funding Proposal (d) Articulating Oral Airway Functional Prototyping [name] MD JK.pdf	Funding Source Grant	1	246 E k	04/18/17

GAP funding proposal (part 1)	CFR - Code of Federal Regulations Title 21.pdf	Device Documentation	1	266	E k	04/18/17

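### XI.2 words the primary test as equivalence although the title and XI.1 declare non-inferiority, and the 1 ml/kg margin has no sign; the sample size is right and the wording needs correcting

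*Combined protocol and SAP*

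**What the plan says.** Four places point to non-inferiority:

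- The project title (I.2) is "The Articulated Oral Airway as an Aid to Mask Ventilation, a Prospective Interventional, Non-Inferiority Study".
- Section XI.1 states: "We will use non-inferiority testing for the analysis of the primary outcome variable in this study". It accepts the AOA as non-inferior "if the difference in expiratory tidal volume measurements between the two devices is less than 1ml/kg".
- The first sentence of XI.2 repeats that rule.
- Later in XI.2 the follow-on step is introduced with "if the non-inferiority is satisfied, we will also explore the superiority of the AOA to the GDA". Its power is worked out for the case that "the expiratory tidal volumes measured with the AOA are 1.5ml/kg greater than with the GDA".

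The sentence in XI.2 that names the test and the null hypothesis says something else. It names the test and its power as "a paired t-test of equivalence of means with a 0.050 one-sided significance level will have 90% power to reject the null hypothesis that". The null hypothesis that this sentence then sets out is worded as "expiratory tidal volumes with a GDA and AOA are not equivalent (> 1ml/kg difference in expiratory tidal volumes". The inputs given there are 55 patients, an SD of the paired difference of 2.5 ml/kg and a margin of 1 ml/kg; 58 patients are to be recruited to cover 3 protocol failures. The true difference assumed for the power is not stated.

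**The concern.** Non-inferiority and equivalence are different hypotheses. Non-inferiority asks only whether the AOA is worse than the Guedel by less than the margin. Equivalence also requires that it is not better by more than the margin. In the text available, XI.2 is the only place where the primary null hypothesis is written, and it is written as equivalence.

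The margin statements do not settle the matter. Both speak of a difference between the devices of less than 1 ml/kg, without saying which device is subtracted from which and without tying the rule to a confidence limit. The one-sided 0.05 level does not settle it either, because equivalence is usually tested by two one-sided tests, each at that level.

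Two things are at stake. An analyst who follows the XI.2 sentence literally would run a test without the stated power, and a clearly better AOA would be expected to fail it. In addition, the pass/fail rule for the primary outcome is not fixed in writing before the data are seen.

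**Working it through.** **Inputs (XI.2).** Margin 1 ml/kg; SD of the paired difference 2.5 ml/kg; one-sided alpha 0.05; n = 55 evaluable pairs, 58 recruited. Assumption not in the plan: true mean difference 0. Below, d is AOA minus Guedel.

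**1. Plan's figure, read as non-inferiority.** Power is the probability that a noncentral t variable with n - 1 degrees of freedom and noncentrality 1 × √n / 2.5 exceeds t(0.95, n - 1). At n = 55 the noncentrality is 7.416 / 2.5 = 2.966 and the critical value is 1.674.

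| Evaluable pairs | Non-inferiority power |
|---|---|
| 54 | 89.6% |
| 55 | 90.05% |
| 58 | 91.4% |

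So 55 is the smallest number reaching 90%, and the plan's figure is reproduced. The normal approximation, ((1.645 + 1.282) × 2.5 / 1)² = 53.5, rounds up to 54, one fewer than the exact result.

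**2. Same inputs, read as equivalence.** Both one-sided tests must reject. Power was obtained by integrating over the chi-square distribution of the sample variance; at 55 pairs a simulation of 200,000 trials also gave 80.1%.

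| Evaluable pairs | Equivalence power |
|---|---|
| 55 | 80.1% |
| 58 | 82.8% |
| 69 | 89.99% |
| 70 | 90.5% |

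The stated 90% at 55 pairs does not reproduce under this reading.

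**3. What each test does if the AOA is better (n = 55).**

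| True d (ml/kg) | Non-inferiority passes | Equivalence passes |
|---|---|---|
| 0 | 90.05% | 80.1% |
| +0.5 | 99.7% | 42.5% |
| +1.0 | >99.9% | 5.0% |
| +1.5 | >99.9% | 0.09% |

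**4. Compatibility with the superiority step (n = 55, observed SD 2.5).** The standard error is 2.5 / √55 = 0.337.

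- Equivalence requires the observed mean d to lie within ±(1 - 1.674 × 0.337) = ±0.44.
- Superiority requires more than 1.674 × 0.337 = 0.56 (one-sided 0.05) or 2.005 × 0.337 = 0.68 (two-sided 0.05).

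These regions do not overlap. They begin to overlap only if the observed SD falls below √55 / (2 × 1.674) = 2.22 (one-sided) or √55 / (1.674 + 2.005) = 2.02 (two-sided).

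**5. The superiority step behind a non-inferiority gate.** At a true d of +1.5 and n = 55, superiority power is 99.7% (one-sided 0.05) or 99.2% (two-sided 0.05). Both agree with the plan's claim of more than 95%.

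**The case against.** The strongest reply is that this is a slip of terminology in one sentence. XI.1, the section on analysis methods, says non-inferiority; so do the title, the opening of XI.2 and the condition for the superiority step. An analyst would have to override all of them to run an equivalence test. The harmful direction also follows from the wording. The rule names the AOA as the device to be shown non-inferior, I.5 asks whether it works "as well as a Guedel oral airway in patients with risk factors for difficult mask ventilation", and the superiority sentence treats larger AOA volumes as better. Under the declared design none of the plan's numbers changes, and the equivalence figures describe a reading the plan probably never intended. The non-overlap in step 4 is not absolute either: with a true SD of 2.5, an observed SD below 2.22 occurs in about 13% of samples of 55, and one below 2.02 in about 2%. Finally, the attachment list includes a full study protocol that is not among the documents available, although VII.B.11 answers no to a separate written protocol.

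Much of this stands. The intent can be inferred, and a careful statistician would probably choose non-inferiority; the direction is less open than the confidence-limit rule. This limits how serious the point is. It does not remove it: the sentence stating the null hypothesis still contradicts the declared design, and an inferred rule is not a prespecified one. If the attached protocol states the rule correctly, XI.2 still needs to agree with it.

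**Conclusion.** The concern holds. XI.2 describes an equivalence test in a study declared as non-inferiority, and the margin is never given a direction. The sample size is not in error: 55 pairs and 90% power fit the one-sided non-inferiority test and no change to them is needed. The shortfall to 80.1%, and the near-certain failure of an AOA better by 1.5 ml/kg, arise only if the equivalence wording is followed.

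These results rest on the plan's SD of 2.5 ml/kg and one-sided 0.05, and on a true difference of 0, which the plan does not state. That assumption matters: at a true d of -0.25 ml/kg, non-inferiority power at 55 pairs is 71.0%. The point should be fixed before analysis, but it does not threaten the design.

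**What to change.** Reword XI.1 and XI.2 as follows:

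- Define d as AOA minus Guedel expiratory tidal volume in ml/kg.
- State H0: mean d ≤ -1 and H1: mean d > -1.
- Declare non-inferiority if the lower one-sided 95% confidence limit for mean d (the lower bound of the two-sided 90% interval) is above -1 ml/kg. At the planned SD and 55 pairs, this corresponds to an observed mean d above about -0.44.
- Remove the equivalence wording from the test name and the null hypothesis.
- State that the 90% power assumes a true difference of 0.
- Name the level of the superiority test that follows, for example two-sided 0.05 with the lower bound of the 95% interval above 0.

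The figures 55, 58 and 90% stay. The cost is wording in two sections, with no extra patients and no change to procedures. If equivalence is really intended, the power should be restated as about 80% at 55 pairs (70 pairs for 90%), and the superiority step should not depend on passing it.

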VII.E.2 *Describe randomization scheme/assignment including ratio such as 1:1, 2:1 etc.*
This study involves a random allocation, cross-over design. All patients will receive both devices - the randomization will determine which of the devices they receive first. There are two reasons for the randomization: 1) As we are evaluating for blood on the airway upon its removal, the order of placement is important as we can only evaluate the first-placed device (we won't know if blood on the second-placed device is from that device or left over from the first device. 2) Without randomization, the CRNA would not be blinded as they would know which device they are using first and second which could introduce bias.

VII.E.3 *Will any questionnaires, surveys, or written assessments be used to obtain data directly from subjects in this study?*
No

VII.E.5 *Does this project involve creating any audiotapes, videotapes, or photographs?*
Yes

VII.E.6 *Provide a detailed description in sequential order of the study procedures following the consent process - DO NOT cut and paste from the Consent Document.*

Describe study populations separately if they will be participating in different procedures - include CONTROL population if applicable.

DESCRIBE:

- *What subjects will be asked to do/what happens in the study (in sequential order)*
- *The time period over which procedures will occur*
- *The time commitment for the subject for individual visits/procedures*
- *Long-term followup and how it occurs*

A. Staff anesthesiologist will perform an airway exam and note the following

- - Age
 - BMI
 - Presence or absence of beard

- Patient dentition
- History of snoring
- Any formal diagnosis of sleep apnea and CPAP/BiPap use and settings
- Mallampati grade (I-IV)
- Mouth opening (in cm)
- Neck extension (full, limited or none)
- Retrognathia (none, mild, significant)
- Any apparent nasal or oral anatomic abnormalities

B. Operating room preparation (performed by research assistant or study medical student):

- A tongue depressor, AOA, and 100mm Guedel oral airway will be available, but out of sight of the clinical providers
- A 28Fr nasopharyngeal airway and water-soluble lubricant will be set on the anesthesia machine next to the laryngoscopy equipment
- The anesthesia circuit facemask will be opacified by internal application of lip balm (as per pediatric routine)
- A pump for delivery of propofol infusion will be available

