- The anesthesia ventilator will be pre-programmed to Pressure Control mode at 15cm H₂O with a rate of 10 breaths/minute and an inspiratory:expiratory ratio of 1:3
- A video recording device will be available to record data from the anesthetic monitor

C. Induction/Airway Management. On arrival to the operating room:

- 1) Apply standard ASA monitors
- 2) Apply Entropy monitor (measures depth of anesthesia via evaluation of brain EEG and quantitative Train of Four (TOF, routine intraoperative monitor which measures level of paralysis via evaluation of the response to electrical stimulus)monitors
- 3) Pre-oxygenate until end tidal O₂ is >90% or for >3 minutes
- 4) Research assistant will open the randomization envelope but not disclose the randomized device order to the clinical team
- 5) IV Induction: 1-2mg midazolam, 50-100mcg fentanyl, 60-100mg lidocaine and 1-2mg/kg propofol.
- 6) Maintenance of anesthesia: 100mcg/kg/min propofol started at time of induction.
- 7) Once lid reflex is lost, obtain a baseline quantitative train-of-four (TOF) and administer rocuronium 1mg/kg of real body weight
- 8) One-handed mask ventilation (MV), without an oral airway, is initiated by the Certified Nurse Anesthetist (CRNA). If one-handed MV without an oral airway is insufficient to return any EtCO₂, a “two-handed jaw-thrust” technique, without an oral airway, is utilized until paralysis/anesthetic depth measures are met. If two-handed technique is insufficient, the 28Fr nasopharyngeal airway is placed and two-handed technique restarted. If two-handed MV with a 28Fr nasopharyngeal airway does not return any EtCO₂, proceed to step #10.
- 9) Once the quantitative TOF is <20% and Entropy reading is 40-60[3], proceed to step 10
 - If, after 90 seconds, the TOF is not <20%, continue to MV until the TOF is <20%
 - If, after 90 seconds, the Entropy reading is not 40-60, increase propofol by 50mcg/kg/min every minute and continue MV until reading is 40-60
- 10) The CRNA (who is performing MV) is asked to turn away so as to be blinded to oral airway placement order
- 11) The RN research assistant or study medical student (both formally trained, with documentation, in oral airway placement) will place the device randomized to be first using the below methods and then cover the patients nose and mouth with the opacified anesthesia mask
 - Guedel oral airway: Insert with concavity facing upward then turn 180 degrees as advancing the proximal bevel to the level of the teeth

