- AOA: In the “closed” conformation, insert with concavity facing upward then turn 180 degrees as advancing the proximal bevel to the level of the teeth. Once at the level of the teeth, bring proximal ends together to lock in the fully ‘open’ conformation

12) The CRNA will turn back to the patient and secure the anesthesia mask utilizing “2-handed jaw-thrust” technique.

13) The ventilator is turned on and the following data is recorded, via video of the anesthetic monitor, for breaths # 6-10:

-Inspiratory tidal volumes

-Expiratory tidal volumes

-EtCO₂ waveform

Note (a): If EtCO₂ is not achieved after 5 breaths with first device, proceed immediately to step #14

Note (b): No video or images will be taken of the patient or patient identifiers, just the anesthesia monitor and the device randomized to be placed first

14) The CRNA will then turn away from the patient and the RN research assistant or study medical student will remove the oral airway, noting the presence of any blood on the device (first device only)

15) Steps 10-13 will be repeated for the device randomized to be placed second, then the anesthetic will proceed at the discretion of the providers

Note: If EtCO₂ is not achieved after 5 breaths with the second device, the protocol is ended and the ASA Difficult Airway Algorithm is followed

D. Post-operative:

15-45 minutes after "Anesthesia Stop" time, the research assistant or study medical student will:

- Perform an oropharyngeal exam for signs of trauma

- Ask the patient to grade their degree of “sore throat” (subjectively, from 0-10)

E. Data Review:

-The video taken during step 13 above will be uploaded to a password-protected server to which only study personnel will have access. The video will contain no images of the patient or patient identifiers, just the anesthesia monitor and the device randomized to be placed first

-The blinded primary investigator ([name]) will transcribe clinical data (expiratory and inspiratory tidal volumes and EtCO₂ waveforms) from the above video

VII.E.7

Will you attempt to recontact subjects who are lost to follow-up?

No - followup is not required in this study

VII.E.9

Will subjects be provided any compensation for participating in this study?

No

VIII. Risks

VIII.1

What are the risks to subjects including

- emotional or psychological

- financial

- legal or social

- physical?

- Emotional or psychological: None foreseen

- Financial: None foreseen

- Legal or social: None foreseen

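### The randomized device order is not used in the only test named for the primary outcome; estimating the device effect by sequence is a cheap improvement

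*Combined protocol and SAP*

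**What the plan says.** Section VII.E.2 of the combined protocol and SAP describes a crossover: "All patients will receive both devices - the randomization will determine which of the devices they receive first". It gives two reasons for randomizing, attribution of blood to the first device and blinding of the nurse anesthetist. A period effect on tidal volume is not among them. The form item asks for the ratio; the answer gives neither a ratio nor blocking.

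Section XI.1 says only "We will use non-inferiority testing for the analysis of the primary outcome variable in this study", with a limit of 1 ml/kg. The test is named in the power rationale, XI.2: "a paired t-test of equivalence of means with a 0.050 one-sided significance level", with "SD of difference is 2.5ml/kg", 55 evaluable patients and 90% power. A paired t-test is named again for superiority. No section mentions period, sequence or carry-over, so a period term is unstated rather than rejected.

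In VII.E.6 C, step 9 sets a condition before the first device: "Once the quantitative TOF is <20% and Entropy reading is 40-60[3], proceed to step 10". Step 8 has a bypass: "If two-handed MV with a 28Fr nasopharyngeal airway does not return any" end-tidal CO₂, the team goes directly to step 10. Step 15 then says "Steps 10-13 will be repeated for the device randomized to be placed second", so the step 9 check is not among the repeated steps.

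**The concern.** A plain paired t-test pools all AOA minus Guedel differences and ignores order. If second-device measurements differ systematically from first-device ones, AOA-first patients carry that shift with one sign and Guedel-first patients with the other. The shifts cancel only when the two orders are equally frequent.

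Drift is possible here because paralysis and anesthetic depth are checked before the first device but not again before the second, and bypass patients may not have met the thresholds at all. Whatever does not cancel enters the estimate compared with the −1 ml/kg limit, in a direction set by chance. Even with equal orders, drift spreads the pooled differences and widens the plain standard error.

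**Working it through.** **Inputs.** From XI.2: n = 55, SD of the difference 2.5 ml/kg, limit −1 ml/kg, one-sided α = 0.05. The documents give no drift (second minus first device), so 0, 0.25, 0.5 and 1.0 ml/kg are assumed. They give no ratio or blocking either, so simple 1:1 order and the splits 28/27, 30/25 and 32/23 are assumed.

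**1. The plan's own figure.** SE = 2.5/√55 = 0.337 ml/kg. The noncentral t with 54 df and noncentrality 1/0.337 = 2.97 gives 90.05% power at a true difference of 0. The stated 55 patients and 90% reproduce.

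**2. Bias of the plain estimate.** With true difference d, the paired difference has mean d − drift in the n₁ AOA-first patients and d + drift in the n₂ Guedel-first patients. The pooled mean is d + drift × (n₂ − n₁)/55.
- 30/25: the factor is 5/55 = 0.091, so the bias is 0.05 ml/kg at drift 0.5 and 0.09 at drift 1.0.
- 32/23: the factor is 9/55 = 0.164, so the bias is 0.08 and 0.16 ml/kg.

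Under simple 1:1 order, a split at least as uneven as 30/25 has probability 0.59, and as 32/23, 0.28 (two-sided binomial tails).

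**3. Estimate by sequence.** Half the sum of the two sequence mean differences is [(d − drift) + (d + drift)]/2 = d, whatever the split. SE = (SD/2) × √(1/n₁ + 1/n₂), with 53 df. At SD 2.5 and no drift:
- 28/27: SE = 1.25 × √(1/28 + 1/27) = 0.337, power 90.02%.
- 32/23: SE = 1.25 × √(1/32 + 1/23) = 0.342, power 89.3%.

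**4. Type I error for a given split** (true difference −1 ml/kg). For the plain test the residual sum of squares is noncentral chi-square with noncentrality 4 × drift² × n₁n₂/(55 × SD²), integrated numerically. Ranges cover both readings of the SD in step 5.

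| Split | Drift (ml/kg) | Plain test, bias toward AOA | Plain test, bias against AOA | By sequence |
|---|---|---|---|---|
| 30/25 | 0.5 | about 6.1% | about 3.5% | 5.0% |
| 30/25 | 1.0 | about 6.6% | 1.9–2.1% | 5.0% |
| 32/23 | 0.5 | 7.5–7.6% | 2.7–2.8% | 5.0% |
| 32/23 | 1.0 | 9.9–10.2% | 1.0–1.2% | 5.0% |

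Averaged over simple 1:1 order, both tests have 5.0% type I error at every drift.

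**5. Power averaged over simple 1:1 order.** The stated 2.5 ml/kg can be the SD of all paired differences (the plainer reading, giving a within-sequence SD of √(2.5² − drift²)) or the within-sequence SD itself.

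| Drift (ml/kg) | All differences: plain | All differences: by sequence | Within sequence: plain | Within sequence: by sequence |
|---|---|---|---|---|
| 0 | 90.0% | 89.5% | 90.0% | 89.5% |
| 0.25 | 90.0% | 89.8% | 89.8% | 89.5% |
| 0.5 | 90.0% | 90.6% | 89.0% | 89.5% |
| 1.0 | 90.0% | 93.6% | 85.9% | 89.5% |

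The two analyses break even at a drift of 0.35 ml/kg on either reading. At a 28/27 split they break even at about 0.09 ml/kg, and the cost at zero drift is 90.05 − 90.02, or about 0.02 points.

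**The case against.** The strongest reply is that this is a choice between two valid analyses. Randomizing order already protects against a period effect, and the plain test holds 5% on average. That is correct.

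The harm also rests on a drift the documents do not supply, and there is reason to expect a small one. The ventilator settings are fixed, "with a rate of 10 breaths/minute and an inspiratory:expiratory ratio of 1:3", and ten breaths at that rate take about one minute per device. The bypass applies only to patients in whom every earlier mask technique returned no CO₂, so it cannot carry a general drift. A drift of 1.0 ml/kg equals the whole non-inferiority limit. At 0.25 ml/kg the plain test's type I error is only 5.6% or 4.3% at 30/25, and 6.3% or 3.8% at 32/23. Below 0.35 ml/kg under simple randomization, adjustment costs a little power. All of this stands and keeps the point small.

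It is also fair that the split probabilities assume unrestricted randomization, whereas step 4 mentions a randomization envelope that could come from a blocked list. A full study protocol appears in the attachment list (although VII.B.11 answers that there is no separate protocol) and may settle ratio and blocking. And a paired t-test in a power rationale does not exclude a period term in the analysis.

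One reply remains. Non-inferiority is declared once, from one realized split, and average validity does not remove a correctable bias in that split. Blocking alone largely deals with the bias, but the three protocol failures allowed for in XI.2 may fall unevenly. It also does not recover power: on the within-sequence reading at drift 1.0 and a 28/27 split, the plain test has about 86–88% power against about 90% by sequence.

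**Conclusion.** The point holds as an improvement to consider. The sample size is right and the paired t-test is valid averaged over 1:1 order. What is missing from the available text is any use of the randomized order in the primary analysis, together with the ratio and blocking.

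The consequence depends on two things the documents do not give: the drift and the realized split. With small drift or near-equal orders it is negligible. The largest effect shown, a type I error near 10% or near 1%, needs a 1.0 ml/kg drift and a 32/23 split together. On the plainer reading of the SD no planned power is lost, and adjustment is a gain above about 0.35 ml/kg. On the within-sequence reading the plain test falls to 85.9% at 1.0 ml/kg.

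**What to change.** In XI.1, state that AOA minus Guedel will be estimated as the average of the two sequence-specific mean differences (equivalently, a model with device and period), and that non-inferiority requires the lower limit of its one-sided 95% confidence interval to lie above −1 ml/kg. Use the same estimate for the superiority exploration. In VII.E.2, unless the full protocol already does so, state that order is randomized 1:1 in blocks.

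The cost is one or two sentences and one degree of freedom. Order is already recorded, so no new data or patients are needed. If drift is below about 0.35 ml/kg and randomization is simple, up to about 0.5 points of power are lost; at a 28/27 split the loss is 0.02 points. The change removes a common period effect. It does not remove carry-over from the first device that differs between the two devices.
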